5.5. Study or Site Termination

If the Sponsor, the Investigator, the clinical monitor, United States (US) Food and Drug Administration (FDA) or other Competent Authority officials discover conditions during the study indicating that the site's participation should be terminated, this action may be taken after appropriate consultation between the Sponsor and the Investigator. Conditions that may warrant termination of the study include, but are not limited to:

- Discovery of an unexpected, serious, or unacceptable risk to subjects enrolled in the study
- Sponsor's decision to suspend or discontinue testing, evaluation, or development of the study drug
- Investigator's failure to comply with pertinent US FDA or regional Health Authority regulations and ICH (International Conference on Harmonisation of Technical Requirements for Registration of Pharmaceuticals for Human Use) guidelines
- Insufficient compliance with protocol requirements

5.6. Study Treatment

5.6.1. Identity of Investigational Product

The investigational medicinal product is supplied to the pharmacy as quizartinib 30 mg yellow tablets (26.5 mg free base) or 20 mg white tablets (17.7 mg free base) of AC010220•2HCl. All packages are shipped at conditions depicted on the product label.

5.6.1.1. Packaging and Storage

Quizartinib drug will be provided to the site in numbered bottles. Subjects randomized to salvage chemotherapy will receive commercially available chemotherapy.

Quizartinib tablets must be stored appropriately in a locked cabinet/room with limited and controlled access under the recommended storage conditions (store up to 25°C [77°F] and protected from freezing). The storage condition of quizartinib drug bottles must be logged daily. If the storage room/cabinet does not have an automated continuous temperature recording system to record the daily temperature data, daily temperature must be monitored and recorded on a temperature log.

Detailed instructions for the handling of quizartinib can be found in the Pharmacy Manual.

5.6.1.2. Study Drug Accountability

The investigational pharmacy will maintain a record of study drug inventory.

The investigator or designee will maintain subject ID, bottle number, lot number, date dispensed, number of bottles and tablets dispensed and returned on a subject study drug dispensing and accountability log.

5.6.2. Method of Assigning Subjects to Treatment Groups

Upon providing written informed consent and initiation of screening procedures, a unique number will be assigned to each subject. Subjects will maintain this number throughout the study.

Subjects will be randomized into the two treatment groups in a 2:1 ratio (242 quizartinib and 121 salvage chemotherapy) and the randomization will be stratified by prior therapy and response, and pre-selected salvage chemotherapy:

Prior therapy and response:

- Relapsed in ≤ 6 months (not post HSCT)
- Refractory
- Relapsed in ≤ 6 months post allogeneic HSCT

Pre-selected chemotherapy, even for subjects subsequently randomized to quizartinib:

- High intensity chemotherapy (MEC; FLAG-IDA)
- Low intensity chemotherapy (LoDAC)

5.6.3. Selection of Doses in the Study

The full rationale is given in Section 5.2.3.

5.6.4. Selection and Timing of Doses for Each Subject

5.6.4.1. Quizartinib

For subjects randomized to quizartinib the starting dose will be 30 mg/day unless the subject is receiving concurrent therapy with a strong CYP3A4 inhibitor, in which case the starting dose will be 20 mg/day. The dose of quizartinib will be taken in the morning over continuous 28-day cycles. Quizartinib should be taken in the morning. If the subject omits taking quizartinib in the morning, it may be taken later in the day (up to midnight) otherwise the dose is considered missed. If the subject vomits after taking quizartinib, no replacement dose should be given. Criteria for dose escalation or dose reduction are provided in Section 5.6.4.3 and Section 5.6.4.4 respectively.

Quizartinib can be crushed and dissolved in water. The resulting solution can be drawn up in a disposable syringe and administered via polyvinyl chloride or silicone nasogastric tubes. Details can be found in the Pharmacy Manual.

5.6.4.2. Salvage Chemotherapy

The Investigator will pre-select the specific salvage chemotherapy regimen before randomization of each subject. All salvage chemotherapy will be administered during 28-day cycles. The start of Cycle 2 (MEC; FLAG-IDA, or LoDAC) and subsequent cycles (LoDAC) may be delayed for up to 14 days to allow for recovery from toxicity. Dose reductions are allowed for toxicity and must be documented in the source record.

Low Dose Cytarabine (LoDAC)

Cytarabine (20 mg) will be administered twice daily by subcutaneous injection for 10 days (Days 1 through 10) over continuous 28-day cycles. A delay of up to 14 days between cycles is allowed for recovery from toxicity.

MEC Chemotherapy

- Mitoxantrone (8 mg/m²/day) will be administered by 5 minute intravenous (IV) injection for 5 days (Days 1 through 5).
- Etoposide (100 mg/m²/day) will be administered by 1 hour IV infusion immediately after mitoxantrone for 5 days (Days 1 through 5).
- Cytarabine (1000 mg/m²/day) will be administered by 1 hour IV infusion immediately after etoposide for 5 days (Days 1 through 5).

FLAG-IDA Chemotherapy

- G-CSF (300 µg/m²/day) will be administered by 2 hour IV infusion for 5 days (Days 1 through 5) or alternatively, G-CSF (5 µg/kg/day) may be administered SC for 5 days (Days 1 through 5). Additional G-CSF is recommended 7 days after the completion of chemotherapy, until ANC is >0.5×10⁹/L.
- Fludarabine (30 mg/m²/day) will be administered by 30 minute IV infusion for 5 days (Days 2 through 6).
- Cytarabine (2000 mg/m²/day) will be administered by 4 hour IV infusion, beginning 4 hours after the fludarabine infusion, for 5 days (Days 2 through 6).
- Idarubicin (10 mg/m²/day) will be administered over 5 to 10 minutes in a fast-running saline drip for 3 days (Days 2 through 4).

5.6.4.3. Quizartinib Dose Escalation Rules and Definitions

CYCLE 1 DAY 16

For subjects not taking a strong CYP3A4 inhibitor the dose of quizartinib will be increased to 60 mg/day starting on Day 16 if the subject's average QTcF (QT interval corrected with Fridericia's formula), based on triplicate reading, is ≤ 450 msec on and before Day 15.

For subjects taking a strong CYP3A4 inhibitor, the dose of quizartinib will be increased to 30 mg/day providing they meet the above QTcF requirements.

CYCLE 2 DAY 1

Subjects who fail to achieve a CR, CRp or CRi as defined in Section 7.2 after at least one 28-day cycle of therapy, and may undergo dose escalation providing the following criteria are met:

- The subject has not had a Grade 3 or higher, non-hematologic, and related adverse event.
- No increase in QTcF more than 60 msec above baseline.

- The subject must not have aplastic bone marrow at the time of the proposed dose escalation.

In addition, subjects who achieved a response (CR, CRi, CRp, or PR) at any time and who subsequently relapsed may undergo dose escalation provided they meet the same criteria as above.

For subjects not taking a strong CYP3A4 inhibitor the dose of quizartinib will be increased to 60 mg/day.

For subjects taking a strong CYP3A4 inhibitor, the dose of quizartinib will be increased to 30 mg/day providing they meet the above requirements.

Following dose escalation, triplicate ECG determinations should be performed at least once weekly for 2 weeks to monitor QTcF prolongation.

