In subjects receiving a reduced dose of quizartinib, the dose may be re-escalated stepwise from 20 mg to 30 mg to 60 mg, except following Grade 3 QTcF prolongation. If the dose was reduced due to toxicity, all events responsible for dose reduction must have resolved to ≤ Grade 1. If the dose was reduced due to administration of a strong CYP3A4 inhibitor, the prior dose can be resumed when the inhibitor is withdrawn.

If a subject undergoes HSCT, quizartinib should be discontinued 7 days before the start of a conditioning regimen. For a subject who was randomized to and received quizartinib, treatment with quizartinib may be resumed at 30 to 100 days after the transplant. Quizartinib may be restarted if:

- Subject has an ANC > $1 \times 10^9/L$ and platelet count > $50 \times 10^9/L$ without platelet transfusion support within 1 week, or a platelet count > $25 \times 10^9/L$ without platelet transfusion support within 2 weeks prior to first dose.
- Subject does not have (1) active acute, or ≥ Grade 3 graft versus host disease (GVHD) or (2) active GVHD therapy (not prophylaxis) initiation in the preceding 21 days.

Follow-up

After study treatment is discontinued, subjects will be followed for 30 days for safety. Assessment of best response to chemotherapy should be conducted at Day 29 (±14 days) or prior to starting subsequent AML therapy. Subjects will then enter long term follow-up every 3 months for collection of information on subsequent AML treatment, remission status, and survival, including the cause and date of death.

Salvage Chemotherapy

The Investigator will pre-select the specific salvage chemotherapy regimen before randomization of each subject. All salvage chemotherapy will be administered during 28-day cycles. The start of Cycle 2 (MEC, FLAG-IDA, or LoDAC) and subsequent cycles (LoDAC) may be delayed for up to 14 days to allow for recovery from toxicity. Dose reductions are allowed for toxicity but must be documented in the source record.

Low Dose Cytarabine (LoDAC)

Cytarabine (20 mg) will be administered twice daily by subcutaneous injection for 10 days (Days 1 through 10) over continuous 28-day cycles. A delay of up to 14 days between cycles is allowed for recovery from toxicity.

MEC Chemotherapy

- Mitoxantrone ($8 \text{ mg/m}^2/\text{day}$) will be administered by 5 minute intravenous (IV)

injection for 5 days (Days 1 through 5).

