5.6.4.4. Quizartinib Dose Reduction Rules and Definitions

The dose of quizartinib will be reduced stepwise from 60 mg/day to 30 mg/day or from 30 mg/day to 20 mg/day, based on the following criteria:

QTcF (QT interval corrected with Fridericia's formula) Prolongation

- Grade 2 (QTcF average of triplicate readings > 480 msec)
 - The dose will be reduced without interruption.
 - If 20 mg/day is the current dose, dosing will be interrupted for up to 14 days. If QTcF returns to within 30 msec of baseline or ≤ 450 msec within 14 days, treatment may be resumed at 20 mg/day.
- Grade 3 (QTcF average of triplicate readings > 500 msec)
 - Dosing will be interrupted for up to 14 days. If QTcF returns to within 30 msec of baseline or ≤ 450 msec within 14 days, treatment may be resumed at a reduced dose.
 - If 20 mg/day is the current dose, dosing will be interrupted for up to 14 days. If QTcF returns to within 30 msec of baseline or ≤ 450 msec within 14 days, treatment may be resumed at 20 mg/day. If Grade 3 event returns, treatment will be discontinued.
- Grade 4 (QTcF >500 msec or >60 msec change from baseline, and Torsade de pointes or polymorphic ventricular tachycardia or signs/symptoms of serious arrhythmia)
 - Treatment will be discontinued.

See Section 8.5 for clinical guidelines for the management of QT prolongation.

Non-hematologic Toxicity

Grade 3 or 4 related to quizartinib and persisting >48 hours without improvement to \leq Grade 2.

- Dosing will be interrupted for up to 14 days.

- If toxicity improves to \leq Grade 1 within 14 days, treatment may be resumed at the reduced dose.

Myelosuppression

In a subject with CRp or CRi, the dose may be reduced at the Investigator's discretion if:

- The subject has been treated for a minimum of 2 cycles.
- Platelet count is $<100 \times 10^9/L$ and ANC is $\leq 1000 \times 10^9/L$.
- Marrow blast count is $<5\%$.
- There is no evidence of extramedullary disease.

Initiation of concomitant treatment with a strong CYP3A4 inhibitor is identified in [Appendix 1: List of Potential QT Prolonging Drugs, CYP3A4 Inhibitors/Inducers, and P-glycoprotein Inhibitors/Inducers](#).

The dose will be reduced one level (60 mg to 30 mg or 30 mg to 20 mg) when treatment with a strong CYP3A4 inhibitor is initiated.

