- A subject taking a strong CYP3A4 inhibitor at enrollment will initiate quizartinib administration at 20 mg/day. The dose will be escalated to 30 mg/day at day 16 if the QTcF interval is less or equal to 450 msec prior to or at the day 15 ECG evaluations.

Subjects receiving a reduced quizartinib dose may be re-escalated one level to 30 mg/day or to 60 mg/day except for reductions due to Grade 3 QTcF prolongation. If the dose was reduced for toxicity, all events responsible for dose reduction must have resolved to \leq Grade 1. If the dose was reduced for a strong CYP3A4 inhibitor, the prior dose of quizartinib may be resumed when the inhibitor is withdrawn.

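### After relapse, a subject on a reduced dose of 20 mg/day without a strong CYP3A4 inhibitor falls under two conflicting rules: Section 5.6.4.3 gives 60 mg/day, Section 5.6.4.4 gives one level

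*Combined protocol and SAP*

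**What the plan says.** **Escalation rule.** Section 5.6.4.3, under its Cycle 2 Day 1 heading, covers subjects without CR, CRp or CRi after at least one cycle. It extends the same criteria to subjects who responded at any time and then relapsed. It gives two target doses:

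- Without a strong inhibitor: "For subjects not taking a strong CYP3A4 inhibitor the dose of quizartinib will be increased to 60 mg/day".
- With one: "For subjects taking a strong CYP3A4 inhibitor, the dose of quizartinib will be increased to 30 mg/day providing they meet the above requirements".

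Neither sentence mentions the current dose. The synopsis (Study Treatment, Cycle 2 Day 1) carries the same two targets. Table 3, footnote j, sends relapsed subjects to Section 5.6.4.3 for the escalation criteria and does not mention Section 5.6.4.4.

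**Re-escalation rule.** Section 5.6.4.4 sets the ladder: "The dose of quizartinib will be reduced stepwise from 60 mg/day to 30 mg/day or from 30 mg/day to 20 mg/day". For the way back up it says: "Subjects receiving a reduced quizartinib dose may be re-escalated one level to 30 mg/day or to 60 mg/day". The synopsis, in the paragraph after its own reduction rules, says that "the dose may be re-escalated stepwise from 20 mg to 30 mg to 60 mg, except following Grade 3 QTcF prolongation". Both places require that the events behind a toxicity reduction have resolved to Grade 1 or less. Both also allow the prior dose to be resumed when a strong inhibitor is withdrawn.

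The synopsis therefore contains both rules, and no section ranks one above the other.

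**The concern.** A relapsed subject on a reduced dose is covered by both rules, and they name different doses. Two sites that each follow the protocol could give the same subject doses that differ 2-fold.

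The main stake is safety, because Sections 3.3 and 5.2.3 describe QTcF prolongation as dose dependent. The second is consistent delivery of the test treatment. A minor consequence concerns the per-protocol set. Section 14.7 lists an incorrect study drug dose as an example of a protocol deviation, so a dose given under either rule could be logged as one. If it were classed as major, Section 13.4 would remove the subject from that set.

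**Working it through.** No sample size, power or alpha figure enters this point, so there is no design figure to reproduce. The check has three parts.

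**1. Compare the rules by current dose.** The levels are 20, 30 and 60 mg/day (Section 5.6.4.4). Subjects on a strong inhibitor begin at the lowest level, "in which case the starting dose will be 20 mg/day" (Section 5.6.4.1).

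| Current dose | Strong inhibitor | Section 5.6.4.3 | Section 5.6.4.4 and synopsis | Conflict in step |
|---|---|---|---|---|
| 30 mg/day | no | 60 (60/30 = 2.0-fold) | 60, one level (2.0-fold) | no |
| 20 mg/day | yes, current | 30 (30/20 = 1.5-fold) | 30, one level (1.5-fold) | no |
| 20 mg/day after a reduction | no | 60 (60/20 = 3.0-fold) | 30, one level (1.5-fold) | **yes** |

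In the third row the resulting doses differ by 60/30 = 2-fold. If the event behind the reduction has not resolved to Grade 1 or less, Section 5.6.4.4 allows no re-escalation, while Section 5.6.4.3 still names 60 mg/day. The doses then differ by 60/20 = 3-fold.

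**2. Check that the third row can be reached.** Section 5.6.4.3 bars escalation after a Grade 3 or higher related non-hematologic event, after a QTcF rise of more than 60 msec over baseline, or with an aplastic marrow. An earlier dose reduction is not itself a bar.

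- *Myelosuppression.* "In a subject with CRp or CRi, the dose may be reduced", after at least 2 cycles and subject to count, marrow blast and extramedullary disease conditions. The ladder reaches 20 mg/day either by one step from 30 or by two steps from 60. This hematologic reduction triggers none of the bars. If the subject later relapses, the relapse sentence of Section 5.6.4.3 applies.
- *Grade 2 QTcF prolongation.* This needs a QTcF above 480 msec. With a rise of at most 60 msec, the baseline must exceed 480 − 60 = 420 msec. Entry allows up to 450 msec (exclusion criterion 12), so baselines above 420 and up to 450 msec qualify. On this route Section 8.5 adds one cycle at the reduced dose before re-escalation, a condition that Section 5.6.4.3 lacks.

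**3. Gauge what a 2-fold difference means.** Section 3.3 reports dose-proportional concentrations from 30 to 90 mg. That range covers both resulting doses, so exposure would also differ about 2-fold. Tables 1 and 2 there give, for the Phase 2b study that randomized subjects to 30 or 60 mg:

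| Maximum QTcF finding | 30 mg (N=38) | 60 mg (N=36) |
|---|---|---|
| Change above 60 msec | 3% | 19% |
| Grade 2 | 5% | 14% |
| Grade 3 | 5% | 3% |

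These figures are by starting dose. Section 5.2.3 says 24 of the 38 subjects who started at 30 mg (63%) later went to 60 mg. The table does not say whether readings after escalation are included, so it is context and not an estimate of risk in the affected group.

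**The case against.** The strongest reply is that these are separate pathways. Section 5.6.4.1 points to Section 5.6.4.3 for escalation and to Section 5.6.4.4 for reduction. Section 6.2.2.5 considers escalation at Cycle 2 Day 1 only if it did not happen at Day 16, Table 3 footnote j treats that visit as a second chance, and Section 5.2.3 describes going from 30 to 60 mg after 15 or 28 days. On that reading 60 mg/day is the target for someone still on the 30 mg starting dose, and the rule worded for reduced doses governs everyone who has been reduced.

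This largely answers the non-response limb. The myelosuppression reduction needs CRp or CRi, so a subject who never achieved CR, CRp or CRi cannot have had it. It does not answer the relapse limb. Section 5.6.4.3 and footnote j admit relapsed subjects without regard to earlier reductions, and the limit on re-escalation sits in the section that sites are told to read for reductions. A reader may well prefer the specific rule, but the text does not say so.

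Other points stand:

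- The myelosuppression example is a pure step-size conflict only if the responsible event resolved to Grade 1 or less before relapse. Otherwise the rules differ on whether the dose may rise at all.
- Escalation is optional in Section 5.6.4.3; only the target dose is fixed.
- Weekly triplicate ECGs for 2 weeks follow any escalation.
- The primary analysis is intention-to-treat on OS, and the per-protocol effect is conjecture, since only major deviations count and nothing shows that following a written rule would be one.

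A reader might infer that every escalated subject, or everyone on 20 mg/day, is sent straight to 60 mg/day, or that the synopsis sides with the one-level rule. The documents support none of this. Subjects on a strong inhibitor have a 30 mg/day target, subjects on 30 mg/day without an inhibitor move one level under both rules, and the synopsis states both rules. Nor is one level an absolute limit, because the prior dose may be resumed when an inhibitor is withdrawn.

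**Conclusion.** Wrong as written: an internal contradiction confined to one group. For a subject on a reduced dose of 20 mg/day, not taking a strong CYP3A4 inhibitor, who relapses after a response, Section 5.6.4.3 gives a 3-fold step with no resolution condition. Section 5.6.4.4 gives a 1.5-fold step, conditional on resolution if the reduction was for toxicity. The resulting doses differ 2-fold when that condition is met.

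The conflict rests mainly on the relapse limb; on the non-response limb the Grade 2 QTcF route remains. Subjects resuming a prior dose after an inhibitor is withdrawn are outside the step-size conflict. The number affected cannot be derived. I would expect it to be small, since reaching 20 mg/day without an inhibitor takes two reductions from 60 mg/day or one from 30. The 2-fold exposure figure assumes that the dose proportionality reported in Section 3.3 holds in these subjects. The point does not bear on the primary OS analysis, and it implies no view on which dose rule is right.

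**What to change.** Reconcile the two synopsis paragraphs (Cycle 2 Day 1 escalation, and re-escalation after a reduction) with Sections 5.6.4.3 and 5.6.4.4. A single wording should state which rule governs a subject on a reduced dose who meets the escalation criteria. It should cover the size of the step and whether the event behind the reduction must first have resolved. Align Table 3 footnote j, and check the same wording against the one-cycle condition in Section 8.5. Which rule applies is the sponsor's clinical decision.

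The cost is a change of protocol wording. No change to sample size, endpoints or analysis is needed.

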20. Medical condition, serious intercurrent illness, or other circumstance that, in the Investigator's judgment, could jeopardize the candidate's safety as a study subject, or that could interfere with study objectives.

21. For subjects in the UK only: Refusal of permission to allow the subject's General Practitioner to be notified of their participation in the study.

STUDY TREATMENT

Quizartinib

For subjects randomized to quizartinib the starting dose will be 30 mg/day unless the subject is receiving concurrent therapy with a strong CYP3A4 inhibitor, in which case the starting dose will be 20 mg/day. The dose will be taken in the morning with or without food over continuous 28-day cycles. If the subject omits to take quizartinib in the morning, it may be taken later in the day (until midnight), otherwise the dose is considered missed. If the subject vomits after taking quizartinib, no replacement dose should be given.

CYCLE 1 DAY 16

For subjects not taking a strong CYP3A4 inhibitor the dose of quizartinib will be increased from 30 to 60 mg/day starting on Day 16 based on the following criteria:

- The subject's average QTcF, based on triplicate reading, must be ≤ 450 msec on and before Day 15.

For subjects taking a strong CYP3A4 inhibitor, the dose of quizartinib will be increased from 20 mg/day to 30 mg/day providing they meet the above QTcF requirements.

CYCLE 2 DAY 1

Subjects who fail to achieve a CR, CRp, or CRi as defined in Section 7.2 after at least one 28-day cycle of therapy may undergo dose escalation if the following criteria are met:

- Subject has not had dose interruption or dose reduction for a Grade 3 or higher, non-hematologic, and related adverse event.
- No increase in QTcF more than 60 msec above baseline.
- The subject must not have aplastic bone marrow at the time of the proposed dose escalation.

In addition, subjects who achieved a response [CR, CRi, CRp or partial remission (PR)] at any time, and who have subsequently relapsed, may undergo dose escalation provided they meet the same criteria outlined above.

For subjects not taking a strong CYP3A4 inhibitor the dose of quizartinib will be increased to 60 mg/day.

For subjects taking a strong CYP3A4 inhibitor, the dose of quizartinib will be increased to 30 mg/day providing they meet the above requirements.

Following dose escalation, triplicate ECG determinations should be performed at least once weekly for 2 weeks to monitor QTcF prolongation.

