- ^h Blood samples for PK determinations will be collected on Day 1 and Day 15 of Cycle 1 before dosing and 1, 2, 4, 6, and 24 hours after dosing. The 24-hour samples must be collected before quizartinib dosing on Day 2 and Day 16. Samples will also be collected on Day 8 of Cycle 1 before dosing and 2 to 4 hours (taken immediately after ECG) after dosing. Thereafter, samples will be collected before dosing and 2 to 4 hours (taken immediately after ECG) after dosing on Day 1 of Cycles 2 and 3. At each time point, 2 mL of blood will be collected. When an ECG is performed at the same study time point, the PK specimen should be taken immediately afterwards.
- ⁱ If consent is provided, blood sample (Pax gene DNA, Pax gene RNA, and PBMC) and buccal swab on Day 1 of Cycle 1 before dosing.
- ^j Quizartinib must be taken at the clinic on Cycle 1: Days 1, 2, 8, 15, and 16; Cycle 2: Day 1; and Cycle 3: Day 1. On other days the subject may take quizartinib at home. Quizartinib should be taken in the morning. Please refer to the dosing guidelines in [Section 5.6.4.3](#) regarding required dose escalation at Day 16 if the subject meets the criteria for dose escalation. A second opportunity for dose escalation is available after the first 28-day cycle if the subject has not achieved a CRc. In addition, subjects who achieved a response (CR, CRi, CRp, or PR) at any time and who subsequently relapsed will be assessed for dose escalation provided they meet the same criteria defined in [Section 5.6.4.3](#).

Table 4 Schedule of Activities and Assessments for Subjects Receiving Quizartinib After HSCT

Activity	Cycle 1 (Post-HSCT)			Cycle 2 and subsequent cycles (Post-HSCT)
	D 1	D 8 ±1	D 15 ±1	D 1 ±3
Physical examination	X ^a	X	X	X
Vital sign determinations	X ^a	X	X	X
ECOG performance status determination	X ^a			X
Assessment of concomitant medications	X ^a	X	X	X
12-lead ECG (triplicate)	X ^b	X ^b	X ^b	X ^b
Pregnancy test for women of childbearing potential	X ^c			X ^c
Clinical laboratory tests (hematology; chemistry; urinalysis)	X ^a	X	X	X
Bone marrow aspiration or biopsy	X ^d			X ^d
Specimen collection for central laboratory assessment of FLT3 mutations using bone marrow	X ^e			
AE/SAE assessment	X	X	X	X
Administration of quizartinib at the study site	X ^f	X ^f	X ^f	
Review of returned study medication and assessment of compliance		X	X	X

^a Performed before dosing and results reviewed before dosing. Blood draws may be taken previous day.

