6.2.2.3. Cycle 1, Day 15 (± 1 day)

The following activities will take place during this visit:

- Physical examination
- Vital sign determinations
- Review of concomitant medications
- 12-lead ECG before dosing and 2, 4, and 6 hours after dosing
- ECG review to determine if dose escalation is required:
- Please refer to Section 5.6.4.3 for dosing guidelines to determine if the subject meets specified criteria for dose escalation; first increased dose to be administered Cycle 1 Day 16.
- Collection of samples obtained before dosing for clinical laboratory tests (hematology, chemistry, and urinalysis)
- AE/SAE evaluation
- Collection of blood samples for PK determinations before dosing and 1, 2, 4, and 6 hours after dosing. When an ECG is performed at the same study time point, the PK specimen should be taken immediately afterwards.
- Administration of quizartinib at the study site
- Review of returned study medication and assessment of compliance

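### Section 5.6.4.3 makes the Day 16 increase to 60 mg/day mandatory on QTcF alone, with no starting dose and no adverse-event condition

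*Combined protocol and SAP*

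**What the plan says.** **Day 16 rule.** Section 5.6.4.3 states that, without a strong CYP3A4 inhibitor, "the dose of quizartinib will be increased to 60 mg/day starting on Day 16 if the" QTcF condition is met (average of triplicates at most 450 msec on and before Day 15). Table 3 footnote j sends the site to 5.6.4.3 "regarding required dose escalation at Day 16 if the subject meets the criteria for dose escalation". The Day 15 visit (6.2.2.3) lists an "ECG review to determine if dose escalation is required". It also lists AE evaluation, but does not link that to the dose decision.

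**Synopsis version.** Here "the dose of quizartinib will be increased from 30 to 60 mg/day starting on Day 16 based on the following criteria", and QTcF is again the only criterion. The synopsis names 30 mg/day as the starting point; 5.6.4.3 does not.

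**After toxicity.** Under 5.6.4.4, a related Grade 3 or 4 non-hematologic event lasting more than 48 hours without improving to Grade 2 or less leads to a hold. If it improves to Grade 1 or less "within 14 days, treatment may be resumed at the reduced dose". A reduced dose "may be re-escalated one level to 30 mg/day or to 60 mg/day except for reductions due to Grade 3 QTcF prolongation", and "If the dose was reduced for toxicity, all events responsible for dose reduction must have resolved to" Grade 1 or less. The synopsis describes the same return as stepwise, 20 to 30 to 60 mg.

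**Cycle 2 Day 1.** Section 5.6.4.3 does have an adverse-event criterion at this later point: "The subject has not had a Grade 3 or higher, non-hematologic, and related adverse event". The synopsis criterion is narrower. It excludes only subjects whose dosing was interrupted or reduced for such an event.

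**The concern.** QTcF addresses one toxicity only. A subject with a severe, drug-related, non-cardiac event in the first two weeks can have a normal QTcF, and the operative section then directs an increase to 60 mg/day.

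What is at stake is patient safety and consistent dosing. In the same situation one site may follow 5.6.4.3 literally and another may hold back. An investigator who sensibly leaves a 30 mg subject at 30 mg/day omits a step that the schedule calls required, and Section 14.7 gives an incorrect study drug dose as an example of a deviation.

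**Working it through.** The plan gives no figure on this point. The check is a comparison of the rules, then an exposure calculation.

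**1. Which early reductions does the Day 16 rule already handle?**
- QTcF reductions: they need QTcF above 480 msec, so they fail the 450 msec test.
- Strong CYP3A4 inhibitor users: they go to 30 mg/day, not 60.
- Myelosuppression reductions: they need at least 2 cycles, so they cannot occur by Day 15.
- Related Grade 3-4 non-hematologic toxicity: not handled.

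**2. Subject (a), already reduced.** Start at 30 mg/day. A related Grade 3 event begins around Days 3-4 and lasts more than 48 hours; dosing is held around Day 6. The event improves to Grade 1 or less and dosing resumes at 20 mg/day around Days 10-12. QTcF stays at or below 450 msec.

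| Rule | Day 16 dose | Step | Force |
|---|---|---|---|
| 5.6.4.3 | 60 mg/day | two levels, 60/20 = 3-fold | mandatory |
| 5.6.4.4 and synopsis re-escalation | at most 30 mg/day | one level, 30/20 = 1.5-fold | optional |

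At Cycle 2 Day 1 (Day 29, and 29 - 16 = 13 days later) the escalation criterion excludes this subject in both 5.6.4.3 and the synopsis.

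**3. Subject (b), still on 30 mg/day.** The related event reached Grade 3 or higher and is unresolved on Day 15. No hold applies, because it has lasted 48 hours or less or has improved only to Grade 2. QTcF is at or below 450 msec. Section 5.6.4.3 gives 60 mg/day. So does the synopsis, since this subject is on 30 mg. The dose doubles under either text. If the event then passes 48 hours, the hold comes after the increase.

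**4. Exposure in the held subject.** Inputs: effective half-life about 3 days and about 4-fold accumulation (Section 3.3). Assumptions: once-daily dosing and linear kinetics. Amount after dose n: x(n) = r·x(n-1) + dose(n), with r = 2^(-1/3) = 0.794. The 30 mg steady state is 30/(1 - r) = 100%.

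Planned Day 15: 1 - 2^(-15/3) = 96.9%. With 60 mg/day on Days 16-28 (13 doses), and 2^(-13/3) = 0.0496:

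Day 28 = 0.0496 × Day 15 + 200% × (1 - 0.0496) = 0.0496 × Day 15 + 190.1%.

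| Schedule to Day 15 | Day 15 | Day 28 at 60 mg/day |
|---|---|---|
| Planned, 30 mg throughout | 96.9% | 194.9% |
| Held Days 5-8, then 20 mg | 58.2% | 193.0% |
| Held Days 5-11, then 20 mg | 45.0% | 192.3% |
| Held Days 8-14, then 20 mg | 26.4% | 191.4% |

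Using the 4-fold accumulation instead, r = 0.75 (half-life 2.41 days) and 0.75^13 = 0.0238, so Day 28 = 0.0238 × Day 15 + 195.2%. The Day 15 values are 98.7%, 60.7%, 48.5% and 25.3%. Day 28 is then about 198% as planned and 196-197% in the held cases. No held case exceeds the planned level.

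**5. Frequency.** The documents give no rate of such events by Day 15. As an assumption only, 1%, 5% or 10% of the 242 quizartinib subjects would be 2, 12 or 24.

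**The case against.** The strongest reply is that an ordinary reading settles subject (a). Section 5.6.4.4 is the specific rule for reduced doses, the synopsis repeats it stepwise, and the synopsis words the Day 16 step as starting from 30 mg/day. That largely shows the intent, and for a reduced subject the optional wording of 5.6.4.4 supports staying at 20 mg/day. But Sections 5.1.2 and 5.6.4.1, Table 3 and the Day 15 visit all send the site to 5.6.4.3, which drops the starting dose, and neither section says which governs. The argument does not reach subject (b), who is on 30 mg.

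Section 5.4.5 requires withdrawal of treatment for an intolerable related event, or when the investigator judges further dosing not in the subject's interest. That stops the drug; it does not provide for staying at the current dose. Section 5.2.3 reports no major adverse-event differences between 30 and 60 mg/day starts. That supports early escalation in general, not in a subject with a current or recent severe related event.

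Some stronger readings are tempting but not supported:
- *A clash with the Grade 1 condition.* Mostly absent for subject (a): resuming at 20 mg/day already requires Grade 1 or less. It arises only if the event worsens again before Day 16.
- *A 4.3-fold or 7.3-fold rise as a measure of harm.* These are 192.3/45.0 and 191.4/26.4. They reflect a low Day 15 denominator.
- *QTcF checked only at low exposure.* In the 7.3-fold case Table 3 schedules a pre-dose ECG on Day 8, at about 1 - 2^(-7/3) = 80% of the 30 mg steady state. ECGs also continue at least weekly for 2 weeks after escalation.
- *Both subjects barred at Cycle 2 Day 1.* Subject (b), never held, is barred by 5.6.4.3 but not by the synopsis.
- *A gap at relapse.* Table 3 footnote j already sends relapse to the 5.6.4.3 criteria.

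**Conclusion.** The point holds as a wording defect with a safety consequence. For subject (a), 5.6.4.3 on its own terms gives 60 mg/day where 5.6.4.4 and the synopsis allow at most an optional 30 mg/day; the synopsis shows the likely intent, but the operative section does not carry it. For subject (b), both texts require doubling the dose during an unresolved severe related event.

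The size is limited. Frequency is unknown and probably low, since for subject (a) onset, persistence, hold, recovery and resumption must all fit before Day 15. On the linear model the held subject's later exposure stays at or just below the planned level. A reader might infer a threat to the trial's conclusions; nothing in the documents supports one, and no effect on OS, alpha or power is claimed. The change should still be made, because the protocol's own later criteria show the caution it intends and the correction is cheap.

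**What to change.** 1. In 5.6.4.3, restore the 30 mg/day starting dose in the Day 16 sentence, as in the synopsis.

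2. In 5.6.4.3 and the synopsis, add under Cycle 1 Day 16:

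> The Day 16 increase applies only to subjects still on their starting dose whose dosing has not been interrupted or reduced for toxicity and who have no related non-hematologic adverse event that reached Grade 3 or higher and has not resolved to Grade 1 or less by Day 15. Subjects whose dose was reduced follow Section 5.6.4.4, one level at a time. Other subjects not escalated on Day 16 for this reason may be escalated once the event has resolved to Grade 1 or less and the QTcF criterion is met.

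3. Apply the same text to the Day 16 step for strong CYP3A4 inhibitor users (5.6.4.4) and to post-HSCT dosing (5.6.4.5). The post-HSCT Day 15 visit (6.2.3.3) already asks whether escalation is appropriate.

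4. Align the Cycle 2 Day 1 adverse-event criterion in 5.6.4.3 with the synopsis (interruption or reduction for such an event), so that a subject who was never held and has recovered is not permanently barred.

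No change to the relapse text is needed.

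Cost: one clarifying amendment. AE evaluation is already done on Day 15, so there are no new visits or tests and no change in sample size. The downside is that a few subjects reach 60 mg/day later; subjects without such toxicity still escalate on Day 16.
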